5.2 Statistical analysis plan

5.2.1 Descriptive statistics

All data collected will be validated and subjected to descriptive case analysis. Categorical, nominal and ordinal variables will be summarised by relative and absolute frequency tables. Continuous variables will be described by mean (and 95% CI), median (and 95% CI), range, standard deviation and coefficient of variation.

5.2.2 Primary Endpoint

The primary endpoint will be assessed by Student's t-test for paired data as already established in the section on sample size.

5.2.3 Secondary End Points

Secondary End Points will consist of evaluating the efficacy, in terms of performance, of MD-Shoulder *Collagen Medical Device* through:

- CMS at months 3, 6 and months 12 compared to day 0, using ANOVA with repeated measures within patient, or Friedman's test.
- NRS at week 2, week 4, months 3, months 6, months 12 compared to day 0 using ANOVA with repeated measures within patient, or Friedman's test.
- ASES and SST at day 0, months 3, months 6 and months 12 using ANOVA with repeated measures within patient, or Friedman's test.

- cuff integrity at day 0 and months 12 by performing MRI of the treated shoulder using Clopper-Pearson binomial test.
- analgesic consumption in the various phases of the study, understood as dosage units/month and evaluated as mean, CI 95% of mean, median, CI 95% of median, SD and range.
- adverse events by records of the various AEs, SAEs, SUSARs according to § 6.4.

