3.5 Participating population

A total of 24 subjects with painful shoulder in rotator cuff tendinopathy will be enrolled. The recruitment phase will be closed no earlier than the number of subjects stipulated in the Clinical Investigation Plan has been reached.

Only subjects will be included:

- belonging to the U.O.C. 1st Orthopedic Clinic (Gaetano Pini Orthopedic Institute, Milan, Italy);
- who meet the inclusion criteria and have no exclusion criteria.

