4.15 Early abandonment of the Clinical Study

I Subjects may leave the Clinical study for the following reasons:

- a. at their own request (even without justification);
- b. at the investigator's discretion.
- c. if they experience an Adverse Event.

The reason for abandonment will be stated in the e-CRF.

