5 STATISTICS

5.1 Sample size

This is a one-sample study. We assume that at baseline the expected mean value of the Constant-Murley score is 65.0 and that given the eligibility criteria this value is between 50 and 80, we can therefore estimate the mean value to be 65.0 ± 7.5 .

It is also expected, that at the end of the treatment i.e. at months 3, using the alternative hypothesis $H_a: \Delta = 13$, compared to the null hypothesis $H_0: \Delta = 0$, estimating that the standard deviation of the differences is $s_{diff} \leq 20$. With these assumptions a sample of 24 patients has a power of 86.2% in discriminating a difference of 13 with a standard deviation of the differences of 20, if a Student's t-test for paired data is used. If the data were not Gaussian distributed, instead of using the nonparametric equivalent (Wilcoxon test, where the power would still be at least 82,8%), we would prefer - if possible - to use a non-linear transformation of the data.

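### The repeated-measures ANOVA and Friedman tests on the secondary scales need every visit, so a subject who leaves after month 3 drops out of those tests and their gains can be biased if leaving depends on response

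*Combined protocol and SAP*

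**What the plan says.** For the secondary scales, section 5.2.3 names two tests without saying when each is used. For CMS it gives "CMS at months 3, 6 and months 12 compared to day 0, using ANOVA with repeated measures within patient, or Friedman's test". For pain it gives "NRS at week 2, week 4, months 3, months 6, months 12 compared to day 0 using ANOVA with repeated measures within patient", again with Friedman's test as the alternative. ASES and SST are treated like CMS. By the visit table (Tab. 1), CMS, ASES and SST are scored at day 0 and months 3, 6 and 12, and NRS also at weeks 2 and 4.

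Section 4.15 lets subjects leave "at their own request (even without justification"), at the investigator's discretion, or after an adverse event. It asks only that the reason be recorded. Nowhere does the plan define an analysis set, a missing-data rule, a mixed model or a sensitivity analysis for missing scores.

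Two other sections bear on the point. Section 5.2.1 summarises all collected data descriptively. Section 5.2.2 says "The primary endpoint will be assessed by Student's t-test for paired data", and that test needs only day 0 and month 3.

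**The concern.** Classical repeated-measures ANOVA and Friedman's test both work on a complete row per subject. Someone seen at day 0 and month 3 who then leaves has no complete row for any of the four scales, and so contributes nothing to these tests even at visits that were attended. For NRS, missing any one of six visits is enough.

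Two things are at stake. First, CMS at month 3 against day 0 is both the primary endpoint and part of the secondary CMS analysis. The paired t-test keeps the leaver and the repeated-measures test does not, so one report could give two month-3 CMS gains from different sets of subjects, with no rule to reconcile them. Second, if those who gain little leave more often, the secondary tests describe those who did well. With a single arm, no between-group contrast could offset this.

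**Working it through.** **Plan's own figure.** Section 3.5 says "A total of 24 subjects with painful shoulder in rotator cuff tendinopathy will be enrolled", and section 5.1 states "a sample of 24 patients has a power of 86.2"% for "discriminating a difference of 13 with a standard deviation of the differences of 20", "if a Student's t-test for paired data is used". Alpha is not stated; two-sided 0.05 is assumed. The noncentrality is 13/20 × √24 = 3.184 with 23 degrees of freedom, and the exact noncentral-t power is 86.2%. The figure is reproduced. The 24 enrolled are the same 24 used for power, so there is no dropout allowance.

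**What one leaver after month 3 removes from the named tests.** Two scores each for CMS, ASES and SST, and four for NRS (day 0, weeks 2 and 4, month 3): 2 + 2 + 2 + 4 = 10 recorded scores.

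**Loss of precision alone.** The documents give no dropout rate, so 10%, 20% and 30% are assumed. The same power formula, applied to one pairwise comparison at 13/20 among completers, gives:

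| Completers | Power |
|---|---|
| 24 | 86.2% |
| 22 (10% leave) | 82.8% |
| 19 (20% leave) | 76.4% |
| 17 (30% leave) | 71.1% |

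For NRS, an assumed 5% missing at each of the five post-baseline visits, independent between visits, leaves 24 × 0.95^5 = 18.6 complete subjects.

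**Bias.** Simulation of 20,000 trials of 24 subjects. The gain of 13 and SD of 20 come from section 5.1, where they refer to month 3. Applying them at months 6 and 12 is an assumption, as is the correlation of 0.7 between the gains at different visits. Two, four or six subjects leave for good after month 3, drawn with weight exp(−b × month-3 gain/20). One SD is 20 points, so leaving is e^b times likelier per SD smaller gain: b = 0.5 gives 1.65 and b = 1 gives 2.72. Mean gain among completers, true value 13:

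| Leaving likelier per SD smaller gain | Visit | 2 leave | 4 leave | 6 leave |
|---|---|---|---|---|
| Unrelated to outcome | months 3 and 12 | 13.0 | 13.0 | 13.0 |
| 1.65 times | month 3 | 13.8 | 14.7 | 15.7 |
| 1.65 times | month 12 | 13.6 | 14.2 | 14.9 |
| 2.72 times | month 3 | 14.6 | 16.1 | 17.7 |
| 2.72 times | month 12 | 14.1 | 15.2 | 16.3 |

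The month-12 excess is about 0.7 times the month-3 excess, as the correlation implies: with four leavers at 2.72, (16.1 − 13) × 0.7 = 2.2, hence 15.2.

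**With all observed scores.** At month 3 everyone is observed, so the estimate stays at about 13.0. At month 12, a regression on the month-3 gain, standing in for a likelihood model, also returns about 13.0 in every row.

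**The case against.** A reader might infer that a leaver's scores are lost to the trial. The documents do not support that: section 5.2.1 still summarises them, and the primary paired t-test keeps anyone seen at day 0 and month 3. The loss is confined to the tests in 5.2.3, and departures after month 3 leave the primary result untouched.

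A reader might also infer that the secondary gains will be overstated. Nothing in the documents says who leaves or how many. If leaving is unrelated to outcome the bias is zero, and if good responders leave, for example because they feel well, its sign reverses.

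The choice of test is not the whole cause. Only the month-3 bias comes from deleting observed scores. At month 12 the leavers have no score, so a plain mean or a paired test at that visit would carry the same bias. What removes it in the simulation is a model that uses the earlier scores, and the plan names none.

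Finally, the plan does not state that incomplete subjects are excluded, and a repeated-measures ANOVA could be fitted as a mixed model. That is fair, but the plan does not say so. The choice would be left until the data are seen, and Friedman's test in its classical form has no such reading.

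These objections narrow the point. They do not remove it: the named methods need complete rows, leavers are foreseen, and no rule covers them.

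**Conclusion.** The point holds for the secondary tests of CMS, NRS, ASES and SST. In their classical form they drop a subject who leaves after month 3 from every visit. The secondary month-3 CMS comparison can then rest on fewer and different subjects than the primary one, and the gains can be biased if leaving depends on response.

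With four of 24 leaving, the excess over a true gain of 13 is nil when leaving is unrelated to outcome. It is about 1.7 points at month 3 and 1.2 at month 12 when leaving is 1.65 times likelier per SD, and about 3.1 and 2.2 points at 2.72 times. These sizes are illustrations: they rest on the assumed number of leavers, mechanism and correlation, and on carrying the month-3 gain and SD to later visits. The need for complete rows does not depend on those assumptions. The point concerns secondary endpoints of a single-arm pilot, and is worth correcting because the correction is cheap.

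**What to change.** In section 5.2.3, make the main analysis of CMS, NRS, ASES and SST a mixed model for repeated measures:

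- Visit as a categorical effect, with contrasts of each later visit against day 0.
- Restricted maximum likelihood with Kenward-Roger degrees of freedom.
- Every observed score of every treated subject, whether or not the subject later left.
- Unstructured covariance for the four-visit scales (4 × 5/2 = 10 parameters). For NRS, an unstructured matrix would need 6 × 7/2 = 21 parameters from 24 subjects, so pre-specify a simpler structure, for example heterogeneous first-order autoregressive, with compound symmetry if that does not converge.
- A non-parametric sensitivity analysis for clearly non-normal scores, such as the Wilcoxon signed-rank test of each visit against day 0 on all available pairs.
- The number of subjects contributing at each visit.

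No extra subjects, visits or data are needed. The cost is a short amendment, which section 6.2 sends to the Ethics Committee. The model assumes that missing scores are explained by the observed ones; this is weaker than what the complete-case tests need, but it cannot be checked from the data. It also relies on approximate normality for bounded scores, which is why the non-parametric analysis should stay.

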3.3 Clinical study Design

This single-center pilot Study Clinical Investigation will be based on a One sample design. Variables will be assessed at 6 different times: at baseline (T0 time), after 2 weeks (T2w), after 4 weeks (T4w), after 3 months (T3months), after 6 months (T6/FU), and after 12 months (T12/FU) i.e., 11 months after the end of infiltrative treatment.

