4.13.3 Secondary End Points

The Secondary Endpoints will consist of evaluating the performance of MD-Shoulder *Collagen Medical Device* through:

- CMS at months 3, 6 and months 12 compared to day 0.
- NRS at week 2, week 4, months 3, months 6, months 12 compared to day 0
- ASES, SST and ROM at months 3, months 6, months 12 compared to day 0
- cuff integrity at months 12 compared to day 0 by performing MRI of the treated shoulder
- analgesic consumption at various phases of the study.
- evaluation of Adverse Events.

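### Secondary scales are defined as changes from day 0, but section 5.2.3 spells out no day-0 contrast or CI of change and gives ROM no analysis

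*Combined protocol and SAP*

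**What the plan says.** All references are to the combined protocol and SAP.

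- **Endpoint definition (4.13.3).** CMS, NRS, ASES, SST and ROM are each named visits set against day 0. For three of them the wording is "ASES, SST and ROM at months 3, months 6, months 12 compared to day 0". The data-collection table (Tab. 1) confirms that ROM is recorded at T0 and at months 3, 6 and 12.
- **Analysis (5.2.3).** CMS: "CMS at months 3, 6 and months 12 compared to day 0, using ANOVA with repeated measures within patient". NRS: "NRS at week 2, week 4, months 3, months 6, months 12 compared to day 0 using ANOVA with repeated measures within patient". ASES and SST: "ASES and SST at day 0, months 3, months 6 and months 12 using ANOVA with repeated measures within patient". Each line offers Friedman's test as the alternative. The ASES/SST line drops the reference to comparison with day 0, and ROM is absent from the section.
- **Nearby cover.** Section 5.2.2: "The primary endpoint will be assessed by Student's t-test for paired data"; this is CMS at month 3. Section 5.2.1: "Continuous variables will be described by mean (and 95% CI), median (and 95% CI), range, standard deviation and coefficient of variation"; within-patient change is not mentioned.
- **Follow-up (3.3).** The last visit falls "11 months after the end of infiltrative treatment".

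**The concern.** The endpoints ask, visit by visit, how far patients are from where they started. A repeated-measures ANOVA or Friedman test, taken alone, asks whether any of the visits differ from one another. It gives neither the size of the change at a given visit nor its uncertainty.

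This matters most for durability. Patients are followed to month 12, and section 6.7 wants reliable conclusions on efficacy from the final report. A significant overall result could be read as lasting benefit when the whole difference comes from earlier visits. Which contrasts to run, with what adjustment, and what to do with ROM would be settled after the data are seen.

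**Working it through.** **1. Match each endpoint to its analysis.**

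| Scale | Visits vs day 0 (4.13.3) | Method in 5.2.3 | Day-0 contrast stated elsewhere |
|---|---|---|---|
| CMS | 3, 6, 12 months | ANOVA or Friedman | month 3 only (5.2.2) |
| NRS | 2, 4 weeks; 3, 6, 12 months | ANOVA or Friedman | none |
| ASES | 3, 6, 12 months | ANOVA or Friedman | none |
| SST | 3, 6, 12 months | ANOVA or Friedman | none |
| ROM | 3, 6, 12 months | none | none |

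Counting ROM as one measure, there are 3 + 5 + 3 + 3 + 3 = 17 comparisons. Removing CMS at month 3 leaves 16 without a stated contrast or CI of change.

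**2. Reproduce the plan's own figure.** Section 5.1 gives n = 24 and a power of 86.2% for "discriminating a difference of 13 with a standard deviation of the differences of 20". Noncentrality = (13/20) × √24 = 3.18, with 23 degrees of freedom. Alpha is not stated; two-sided 0.05 is assumed. The exact paired-t power is then 86.2%, as stated. This concerns the primary test, and nothing below changes it.

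**3. What the overall test can and cannot show.** The documents give no effects, SDs or correlations for the secondary scales, so these are assumptions.

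- *NRS, six visits.* n = 24, SD 2, effect of 1.5 points to month 6 and none at month 12, correlation r^(months apart) with r from 0.6 to 0.95. The ANOVA rejects in 98-100% of runs uncorrected and in 95-100% with Greenhouse-Geisser. The month-12 paired t-test rejects in about 5%, its nominal level. Friedman's test, run for effects of 1.5 to 2 points, rejects in 98-100%.
- *Four visits, CMS-like.* SD of differences 20, true changes of 13, 13 and 0 at months 3, 6 and 12, compound symmetry, 4,000 runs. The ANOVA rejects in 96.9%, the month-12 paired test in 4.9%.

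A significant overall test is therefore fully compatible with no change at month 12.

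**4. What a stated paired analysis would deliver.** With all 24 patients, the 95% CI half-width for a mean change is t(0.975, 23) × SD/√24 = 0.42 SD. For CMS, if the SD of 20 also holds at month 12, this is 2.069 × 20/4.899 = 8.4 points.

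**5. Side issues, sized.**

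- *Sphericity.* With pure decay correlation, the type I error of the uncorrected NRS ANOVA is 7.3-10.2%. With part of the variance assigned to stable patient differences and visit-level error, it is 5.0-6.0%. The answer depends on the assumed covariance.
- *Missed visits.* If each post-baseline visit were missed independently with probability 5%, complete rows would number 24 × 0.95^5 = 18.6 for NRS and 24 × 0.95^3 = 20.6 for the four-visit scales. If patients instead leave for good, everyone seen at month 12 has the earlier visits too, and complete rows equal the month-12 pairs.

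**The case against.** The strongest reply is that section 5.2.3 never says the test is only an overall one. For CMS and NRS it couples comparison with day 0 to the ANOVA, and baseline contrasts within that model are a natural reading. Section 5.2.1 also requires descriptive means with 95% CIs, so a return to baseline at month 12 would be visible in the tables, and ROM would be described there too. The simulated scenario was built to have no month-12 effect. This is a 24-patient pilot, and the endpoints are secondary.

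Much of this stands. The fair charge is that the contrasts are not spelled out, not that the plan rules them out. But the favourable reading does not reach ASES and SST, where the reference to day 0 is missing, or ROM, which has no line at all. A CI around a visit mean is not a CI for paired change. The simulation shows what an overall test can establish; it does not predict what the report will claim.

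A reader might also infer that the plan carries a type I error near 10%, or that it loses a large share of its patients to incomplete rows. The documents support neither. The first depends on the covariance assumed. The second applies to intermittent missed visits, whereas section 4.15 speaks only of patients leaving the study, which does not widen the month-12 interval.

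**Conclusion.** The concern holds as a gap between endpoint and analysis. Sixteen comparisons that the plan itself defines (CMS at months 6 and 12; NRS at five visits; ASES, SST and ROM at three each) have no stated contrast with day 0 and no CI of change, and ROM has no named analysis beyond general description. The textual finding needs no assumption. The 95-100% against about 5% illustration rests on the assumed NRS effect, SD and correlations.

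It would go too far to infer that the plan will produce a false claim of lasting benefit, or that the primary result is compromised. The primary paired t-test and its 86.2% power are untouched. Nor would a significant month-12 paired test attribute the change to the device, since the study has one group. Sphericity and complete-row loss are minor, assumption-dependent points and should not be reported as errors of the plan.

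**What to change.** In section 5.2.3, state that for CMS (months 6 and 12), NRS (all five post-baseline visits), and ASES, SST and each ROM measure (months 3, 6 and 12):

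- the analysis is the mean within-patient change from day 0 with 95% CI, by paired t-test, on all patients observed at that visit;
- if the changes are not Gaussian, the order in section 5.1 applies: a transformation if possible, otherwise the paired Wilcoxon test with the Hodges-Lehmann estimate and its CI;
- the comparisons are labelled exploratory in advance (Holm adjustment within each scale is an acceptable alternative);
- the number of patients observed is reported at each visit;
- if the ANOVA is kept as an overall test, it uses the Greenhouse-Geisser correction.

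**Cost.** SAP wording and a little analysis; no extra patients or visits. Holm, if chosen, costs some power: with CMS gains of 13 at both months 6 and 12, SD 20, n = 24 and correlation of changes 0.3-0.7 (assumed), month-12 power falls from 86% to about 82-84%.

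Paired change is biased if dropout depends on earlier response. If 20-40% of patients gaining under 13 CMS points at month 3 left (assumed; true gain 13), the month-12 paired mean would be 13.5-15.8, against 12.9-13.1 from a likelihood analysis of all observed data. A likelihood-based mixed model, which relies on data missing at random, may therefore be added as a sensitivity analysis.

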3.6 Enrollment

Enrollment will begin only after approval of the Clinical Investigation Plan by the ASST Istituto Ortopedico Gaetano Pini Ethics Committee and notification of the study at the Ministry of Health.

Enrollment will involve subjects with rotator cuff syndrome who are eligible according to the selection criteria. Diagnosis will be performed by the Principal Investigator through clinical examination and instrumental investigation with shoulder MRI. The MRI examination must be recent and of good quality; if the subject does not have it, an MRI examination will be performed before diagnosis and enrollment. Eligible subjects will be explained by the Co-Investigator the rationale for the Clinical Investigation Plan and the procedures involved. Consent to participate in the study will then be sought.

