3.6.1 Selection Criteria

3.6.2 Inclusion Criteria

- Subjects with age > 18 years;
- Subjects with shoulder pain for at least 3 month;
- Subjects with a diagnosis of rotator cuff tendinopathy, subacromial conflict syndrome, partial rotator cuff tendon injuries (injuries A and B according to Snyder's Classification);
- Subjects with a CMS score between 40 and 75;
- Subjects who understood and signed the informed consent for active participation in the study;
- Subjects who are able to understand the conditions of the study and take part throughout the duration of the study.

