3.6.3 Exclusion Criteria

- Subjects with complete rotator cuff injuries (C injuries according to Snyder's classification);
- Subjects with shoulder instability;
- Subjects with adhesive retractile capsulitis;
- Subjects undergoing HA and/or cortisone infiltration in a period < 3 months;
- Subjects with diabetes mellitus;
- Subjects with uncontrolled thyroid disease;
- Subjects with coagulopathies;
- Subjects on chronic treatment with immunosuppressants;
- Subjects with allergy to porcine collagen;
- Subjects in pregnancy or lactation.

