- CMS assessment;
- NRS assessment;
- ASES assessment.
- SST assessment;
- shoulder ROM assessment;
- assessment of pain killer drug consumption used in case of pain onset through clinical diary;
- evaluation of any Adverse Events.

T6/FU (±7days):

At 6 months from day 0, we will again proceed with the assessment of the End Points stipulated in the Clinical Investigation Plan.

Including:

- CMS assessment;
- NRS assessment;
- ASES assessment.
- SST assessment;
- shoulder ROM assessment;
- assessment of painkiller drug consumption used in case of pain onset

- through clinical diary;
- evaluation of any Adverse Events.

T12/FU(±7days):

At 12 months from day 0, i.e at the end of the Clinical Investigation, all the End Points set out in the Investigation Plan will be re-assessed.

Including:

- CMS assessment;
- NRS assessment;
- ASES assessment.
- SST assessment;
- shoulder ROM evaluation;
- MRI assessment;
- painkiller drug consumption assessment used in case of pain onset

through clinical diary;

- evaluation of any Adverse Events;

Diagnosis, evaluation of inflammatory and degenerative signs at MRI investigation of the shoulder with rotator cuff syndrome will be performed by the Principal Investigator.

The CMS, ASES, SST rating scales will be administered to the subject by the Co-Investigator. Recording of the clinical diary data regarding painkiller medication intake will be performed by the Co-Investigator.

The occurrence of Adverse Events will be assessed at each visit. All Adverse Events (AEs), Serious Adverse Events (SAEs) and Suspected Serious and Unexpected Adverse Reactions (SUSARs) occurring between the date of signing the Informed Consent and the end of the Clinical Investigation will be recorded and reported.

All data collected will have to be entered by the Data Manager in the Electronic Data Collection Form (e-CRF) provided by Guna S.p.a. The Principal Investigator and the Data Manager identified by him will be responsible for the correct entry of the collected data in the e-CRF.

In particular, it is planned to obtain a data collection that is schematically described in the following table (Tab. 1), which shows the entries to be made at each visit:

EXPERIMENTAL PROCEDURES	VISIT T0 Enrollment	VISIT T2weeks ± 2days	VISIT T4weeks ± 2days	VISIT T3 months ± 7days	VISIT T6/FU ± 7days	VISIT T12/FU ± 7days
Diagnosi clinica RCS	X					
Valutazione criteri di selezione	X					
Signing Informat consent	X					
Signing of privacy agreement	X					

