4.11 Study group

Only one experimental group is included in the investigation plan, which will be treated with 2 ml volume ultrasound-guided infiltrations of MD-Shoulder *Collagen Medical Device* (GUNA, Milan-Italy). Composition per 2 ml: collagen 100 micrograms.

Excipients: Iris, NaCl, Water for injection. Subjects will be treated with no. 1 ultrasound infiltration at the time of enrolment, 2 weeks after enrolment and 4 weeks after enrolment.

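### MRI cuff integrity is compared within patients, but section 5.2.3 names a one-proportion test and does not define integrity, the proportion tested or the null

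*Combined protocol and SAP*

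**What the plan says.** - **Endpoint.** Section 4.13.3 lists "cuff integrity at months 12 compared to day 0 by performing MRI of the treated shoulder". The data collection table in section 4.9.2 schedules MRI at T0 and T12 only. Section 4.11 states that "Only one experimental group is included in the investigation plan". Each patient with both scans therefore gives one pair of readings.
- **Analysis.** Section 5.2.3 gives "cuff integrity at day 0 and months 12 by performing MRI of the treated shoulder using Clopper-Pearson binomial test". It does not say what counts as intact, which proportion is tested, against what value, or whether the pairs are used.
- **Neighbouring analyses.** The same list specifies within-patient repeated measures for CMS, NRS, ASES and SST, and section 5.2.2 names a paired t-test for the primary endpoint.
- **Descriptive plan.** Section 5.2.1 says "Categorical, nominal and ordinal variables will be summarised by relative and absolute frequency tables". It does not mention a cross-table of the two visits.
- **What could define the reading.** Sections 3.6.2 and 3.6.3 use a graded lesion classification for eligibility: partial tears (A and B) are admitted and complete tears (C) are excluded. Section 4.9.2 describes the MRI work as "Diagnosis, evaluation of inflammatory and degenerative signs at MRI investigation of the shoulder with rotator cuff syndrome". Neither is linked to cuff integrity.

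**The concern.** Clopper-Pearson is the exact interval, with a matching binomial test, for a single proportion. The endpoint is a change between two readings on the same patient. The plainest reading of section 5.2.3 is a proportion at each visit, and that does not test within-patient change. A second reading, month 12 against a fixed value, has the same limitation and also needs a null that the plan does not state.

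MRI cuff integrity is the plan's structural outcome. Under either reading, patients whose cuff deteriorated can be offset by others who improved, and the report would show only the balance. The undefined reading adds to this, because different meanings of integrity call for different analyses.

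**Working it through.** **Inputs.** n = 24 (sections 3.5 and 5.1), with MRI at day 0 and month 12 (section 4.9.2). The plan gives no expected integrity rate, discordance or power for this endpoint, so there is no figure of its own to reproduce; the power in section 5.1 concerns the CMS. The counts below are assumed for illustration, with all 24 patients having both scans, and tests are two-sided at 0.05 (also assumed).

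**Formulas.**
- Clopper-Pearson 95% limits for x of n: lower = Beta quantile(0.025; x, n − x + 1); upper = Beta quantile(0.975; x + 1, n − x).
- Exact paired test (McNemar for a yes/no reading): with b improved and c worsened, p = 2 × P(X ≥ max(b, c)), where X ~ Binomial(b + c, 0.5).

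**Step 1: one-proportion readings, 12/24 intact at day 0 and 18/24 at month 12.**
- Separate intervals: 29.1–70.9% and 53.3–90.2%.
- 18/24 against a fixed 0.5: p = 0.023.
- These use only the two totals, so they are the same for every pairing.

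**Step 2: paired reading of the same totals.** The totals force b − c = 6. At most 12 patients can improve, so c runs from 0 to 6.

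| Improved | Worsened | Exact paired p |
|---|---|---|
| 6 | 0 | 2 × 1/64 = 0.031 |
| 7 | 1 | 2 × 9/256 = 0.070 |
| 8 | 2 | 2 × 56/1024 = 0.109 |
| 9 | 3 | 2 × 299/4096 = 0.146 |
| 12 | 6 | 2 × 31180/262144 = 0.238 |

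The proportion worsened runs from 0/24 (95% CI 0–14.2%) to 6/24 (9.8–46.7%).

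**Step 3: other totals, 10/24 to 16/24.**
- Separate intervals: 22.1–63.4% and 44.7–84.4%.
- 16/24 against a fixed 10/24: p = 0.021. Against 0.5: p = 0.152. The unstated null now matters as well; in Step 1 the two nulls coincide because 12/24 = 0.5.
- Exact paired p: 0.031 (6 improved, 0 worsened) to 0.286 (14 improved, 8 worsened).

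**Step 4: limit of the argument.** Keep 12/24 at day 0 and 6 improved, and let 0, 1 or 2 worsen. Month 12 becomes 18, 17 or 16 of 24, and p against 0.5 is 0.023, 0.064 or 0.152. The one-proportion readings do respond to worsening that changes the total. They are blind only to how a given net change is made up.

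**Step 5: integrity read as no complete tear.** Grade C is excluded at entry, so day 0 is 24/24 by eligibility and only the month-12 proportion is unknown. Section 2.2 quotes progression to complete tear at 0.26% per month. Applied to all 24 patients as an assumption, 1 − (1 − 0.0026)^12 = 3.1%, or 24 × 0.031 ≈ 0.7 patients, and the chance of none is 0.9974^288 ≈ 47%. The Clopper-Pearson interval would be 0–14.2% for 0/24, or 0.1–21.1% for 1/24.

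**The case against.** The strongest reply is that the named method can be right.

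- A binomial test on the discordant pairs with null 0.5 is the exact McNemar test.
- If integrity means no complete tear, day 0 is fixed at 100% by eligibility. A single proportion at month 12 is then the correct target and Clopper-Pearson the correct interval. Section 2.2, which speaks of progression to complete injury, makes this a coherent reading.

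Both points stand. A reader might infer that section 5.2.3 prescribes an invalid test; the documents do not support that. They support only that the text does not say which use is meant, and that its plainest reading leaves the pairs unused.

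A reader might also infer that the one-proportion readings give the same answer however many patients worsen. That is not so: Step 4 shows that it holds only when the totals at both visits are fixed.

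Two further replies are fair. The counts are hypothetical, and on the no-complete-tear reading 6 of 24 worsening would be far above the 0.7 implied by section 2.2, so the table shows a mechanism and does not forecast a result. Also, the e-CRF was not among the documents and may hold MRI reading categories. Even if it does, section 5.2.3 would still have to name the reading and the proportion analysed.

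**Conclusion.** The point holds as a minor one. The endpoint is within-patient, and the analysis line names a one-proportion method without defining integrity, the proportion or the null. Under two of the readings that the wording allows, the result reflects only net change. In the illustration, a single one-proportion result (p = 0.023) goes with exact paired p-values from 0.031 to 0.238, and with anything from 0 to 6 patients worsened.

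The figures rest on assumed counts, complete pairs and a two-sided 0.05 level; the mechanism does not depend on the particular counts. The primary endpoint and the sample size are unaffected.

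**What to change.** In section 5.2.3:

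1. Define one integrity reading, used in the same way at both MRIs, and say whether the inflammatory and degenerative signs in section 4.9.2 are part of it. If the reading is graded, state which moves count as improved and worsened.
2. Report the day 0 by month 12 cross-table and the number of patients without a month-12 MRI.
3. Replace the named test with the exact McNemar test (exact sign test of improved against worsened if graded). Keep Clopper-Pearson for the 95% CIs of the proportions improved and worsened.
4. If integrity means no complete tear, report only the month-12 proportion progressing with its Clopper-Pearson CI, and do no test.

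The cost is a few lines of wording and possibly one e-CRF item at each MRI visit, with no extra scans or patients. It is best settled before the month-12 MRIs are read. The downside is low power: at least 6 discordant pairs are needed for two-sided p < 0.05 (5–0 gives 0.063, 6–0 gives 0.031), and one pair in the other direction is tolerated only from 9 discordant pairs (7–1 gives 0.070, 8–1 gives 0.039). The result will be mostly descriptive and should be presented so.
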